## Methodology

### Participants

44 PwMS and 44 healthy controls (40, +10% to cover possible dropouts and missing data) will be recruited from the Flemish MS rehabilitation centers in Melsbroek (NMSC) and Pelt (Noorderhart RMSC), and as well from the REVAL research center in UHasselt and its established network (eg. UMSC Patient Platform). Information flyers will be distributed in the centers and online content via the website and social media of REVAL and the Flemish MS society; no economical compensation will be provided by the research organization to the participants of this study. We will search age and sex-matching subjects for the healthy controls, considering a 5-year range per subject. After giving informed consent, demographics of age and gender, height and weight, years of education, as well as MS-related information such as EDSS, type of MS, use of assistive device for walking in daily life, and years since diagnosis, will be collected and provided by the centers or via self-report. The participants will be instructed to keep their normal routine but to avoid extraneous physical activity at least 24 hours before the data collection session.

- Inclusion criteria for PwMS: age between 18 and 65 years old; a diagnosis of MS (2017 revisions of the McDonalds criteria); ability to walk for 6 minutes without rest and without the need of a walking aid; ability to repeatedly perform the sit to stand transitions on a standard chair (43cm seat height) without hand support. Additionally, no relapses >1 month preceding the start of the study.
- Inclusion criteria for healthy controls: age between 18 and 70 years old, sex- and age-matched on a group level.
- Exclusion criteria: cognitive impairment hindering understanding of study instructions, pregnancy, and musculoskeletal disorders in the lower limbs (not related to MS), cardiovascular red flags for exercise (screened with Physical Activity Readiness Questionnaire), other diagnosis for neurological or metabolic disease limiting the full execution of the tests (eg. peripheral neuropathy altering the foot plantar sensibility).

Inclusion/exclusion criteria will be controlled at the beginning of the first session: the participant will read the criteria presented in the informed consent and will be asked to confirm that he/she can enroll in the study.

[figure not shown]

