#### 6.4 Rate of Perceived Stability \*

Afterwards, the participants will perform the 6 Minute Walk Test (6MWT), walking back and forth in a 30m corridor as fast and safe as possible for 6 minutes, the 30 seconds Chair Stand Test (30CST), repeating STS transitions as fast and safe as possible for 30 seconds, and the Dual Joint Position Test (DJPT), a test for proprioception. (25)

Except for the T25FW, the participant will wear wearable sensors in pre-defined body positions for the gait and STS tests (6 OPALs – APDM technology© IMU sensors: 2 over the dorsal part of the feet, 2 on the lower legs, 1 anterior to the sternum and 1 posterior to the third/fourth lumbar vertebra; 1 Polar H10 chest-band for real-time heart rate monitor).

Figure 4 Wearable sensors placement on the body and working prototype of the force sensing device for perceptive tasks

The perceived fatigue will be asked just before and immediately after the 6MWT and the 30CST using the VAS-F, a 0-10 visual analogical scale for state fatigue.

Figure 5 10 points visual analogic scale for fatigue (VAS-F)

- **Familiarization with motor and perceptive tasks**

At this point the participant will be familiarized with the experimental procedures and the experimenter is defining the ranges of performance variations that will be experimentally-induced in part B. This will happen in the presented order:

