## Data and statistical analysis

Motor performance data (gait and STS kinematic, kinetics and spatial-temporal parameters) will be acquired by wearable sensors and extracted from Moveo software (APDM) as .csv file or raw data, and Matlab scripts will be used in case of parameters requiring specific calculation. Data acquired from the participants reports on their perception, during the experimental tasks in Part A and Part B, will be extracted with dedicated Matlab scripts. Statistical analysis will be performed using SPSS (V. 28.01). Tests of normality (Shapiro-Wilk test) will be used to determine if parametric or non-parametric statistical tests have to be used for the comparisons and correlations. The  $\alpha$  for all analyses will be set at 0,05.

**Clinical assessment** outcomes, with a particular focus on the MAIA-2, ISAQ and PAS scores and subscores, will be compared between groups with an independent T test (or with its non-parametric equivalent Mann-Whitney U-Test), to detect significant differences in the subjective beliefs about perceptive abilities.

In the **experimental Part A** we will obtain the participants' minimal perceptive threshold for self-paced performance variations which will be compared between groups with an independent T test (or with its non-parametric equivalent). We will also relate the frequency of the reports with the measured performance variability (coefficient of variation of the selected motor performance parameter: gait speed or STS duration) to obtain a novel outcome measure reflecting perceptive accuracy. We will study it between and within groups using a mixed model ANOVA with time and group as factors to detect significant differences between PwMS and controls and its variations relative to the accumulation of fatigue during the prolonged motor tasks. To investigate its interference with perceptive accuracy the difference between the subjective rate of fatigue (VAS-F) pre-post task protocols will be included in the analysis as covariate.

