In the **experimental Part B** within-subject correlations will be calculated between the imposed performance in motor tasks and the perception of its variations. These correlations will be examined separately for different phases of each trial to index perceptive accuracy. Fisher Z transformations (or other types of transformations eg. log transformation) will be applied to these correlations before further analysis, with results back-transformed for reporting. We will study it between and within groups using a mixed model ANOVA with time (protocol subphase) and group as factors to detect significant differences between PwMS and controls and its variations relative to the different subphases of the protocol. To investigate its interference with perceptive accuracy the difference between the subjective rate of fatigue (VAS-F) pre-post protocols will be included in the analysis as covariate. The correspondence between measured and reported dimensions of perceptive accuracy will be calculated as their absolute difference and compared between groups using an independent T test (or with its non-parametric equivalent).

Finally, for the accuracy outcomes derived from both experimental parts we will explore correlations, separated per group, to investigate the relationship between objectively measured perceptive accuracy and factors that potentially interfere with it (demographics, questionnaires and clinical assessments). Then, a regression analysis will be performed to assess the strength of these relationships and identify the most important explanatory factors or predictors.

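### State that VAS-F change is centred and how it is crossed with time; if it is entered raw and crossed, the time main effect refers to a participant with no fatigue build-up

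*Combined protocol and SAP*

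**What the plan says.** The Part A paragraph of the section Data and statistical analysis studies the accuracy measure between and within groups, "using a mixed model ANOVA with time and group as factors to detect significant differences between PwMS and controls" and also "its variations relative to the accumulation of fatigue during the prolonged motor tasks". It then adds the covariate: "the difference between the subjective rate of fatigue (VAS-F) pre-post task protocols will be included in the analysis as covariate". The Part B paragraph uses the same model with protocol subphase as the time factor, and the same covariate: "the difference between the subjective rate of fatigue (VAS-F) pre-post protocols will be included in the analysis as covariate".

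Fatigue is rated "using the VAS-F, a 0-10 visual analogical scale for state fatigue", before and after each task. Each participant therefore has one change score per task, constant over the time levels, and zero means no build-up.

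The plan does not say whether the score is entered raw or centred, or whether it is crossed with time or group. It names the package ("Statistical analysis will be performed using SPSS (V. 28.01") but not the procedure. The significance level "for all analyses will be set at 0,05".

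**The concern.** A covariate with one value per person can be related to change over time only through a covariate x time term. Once that term is in the model, the time main effect is conditional: it is the expected change for a person whose covariate equals zero. With a raw VAS-F difference, that is a person who did not tire. The plan's aim is to describe how accuracy varies while fatigue accumulates, so this is an awkward reference point.

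Two things follow if the average VAS-F change is above zero. The standard error of the time effect grows, because the effect is estimated away from the centre of the data. And if people who tire more also lose more accuracy, the estimate itself moves towards no decline, or past it to an apparent improvement. The data would be sound, but the within-group statement about time would not describe the average participant.

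**Working it through.** **Sample size.** The plan recruits "44 PwMS and 44 healthy controls (40, +10% to cover possible dropouts and missing data": 40 x 1.10 = 44 per group, as stated. The calculations use the 40 + 40 = 80 expected to be analysed. The base of 40 cannot be rederived, because no effect size, SD or power is given.

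**Assumed inputs (not in the documents).** VAS-F change SD 1.5; mean VAS-F change m of 0, 0.5, 1 or 2, equal in both groups; accuracy contrast over time with SD 1 and average -0.3; correlation r between VAS-F change and that contrast of 0 or -0.3; two-sided 0.05.

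**Model.** Each time contrast D is regressed on an intercept, effect-coded group and VAS-F change x. The time test is the test of the intercept.
- Slope on x: b = r / 1.5. For r = -0.3, b = -0.2 per VAS-F point.
- Intercept, centred: -0.3. Intercept, raw: -0.3 - b x m.
- SE, centred: sqrt(1 - r^2) / sqrt(80), which is 0.1118 for r = 0 and 0.1067 for r = -0.3.
- SE, raw: the centred SE times sqrt(1 + (m/1.5)^2), a factor of 1.05, 1.20 and 1.67 for m = 0.5, 1 and 2.

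**Raw entry, r = -0.3** (power by simulation):

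| m | Intercept | SE | Ratio | Power |
|---|---|---|---|---|
| 0 | -0.30 | 0.1067 | -2.81 | as centred |
| 0.5 | -0.20 | 0.1124 | -1.78 | 41% |
| 1 | -0.10 | 0.1282 | -0.78 | 12% |
| 2 | +0.10 | 0.1778 | +0.56 | 8% |

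Centred power is about 78% throughout. Non-central t values agree within about one percentage point (79% centred; 42%, 12% and 9% raw). At m = 2 nearly all of the 8% is in the wrong direction.

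**Raw entry, r = 0.** The intercept stays at -0.3 and only the SE grows. Power is 70%, 59% and 35% at m = 0.5, 1 and 2, against about 75% centred.

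**Full repeated-measures check.** This simulation used 40 per group, six time levels, covariate x time in the model, and assumed mean VAS-F changes of 3 (PwMS) and 1.5 (controls). When the decline was driven wholly by fatigue, the time effect was significant in 5.8% of raw runs, 91.3% of centred runs and 90.8% of runs without the covariate. With mean changes of 2 and 0.5, it was 5.6% raw and 39.3% centred.

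**What does not move.** In those runs the group x time and VAS-F x time p-values were the same with either coding (differences below 1e-13). In one simulated data set with the covariate additive only, the time test was also the same either way (chi-square 17.57, p = 0.0035). With covariate x time added, the same data gave p = 0.169 raw and p = 0.0025 centred, while group x time stayed at p = 0.515.

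**The case against.** The strongest reply is that the plan is silent rather than wrong. A reader might infer that it prescribes the raw score, but it says only that the difference is a covariate. The covariate x time term is not stated either, and with an additive covariate centring is irrelevant to the time test. Both points stand, so this is an unspecified model and not an error in the text. The crossed model is nevertheless the natural reading, because an additive, time-constant covariate cannot show whether fatigue build-up goes with change in accuracy.

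A reader might also infer that the comparison of PwMS with controls over time is compromised. The documents do not support that. The listed hypotheses concern group differences, the last-subphase difference in Part B (a group x time question) and confidence correspondence. None is a time main effect alone, and group x time does not depend on centring. The exception is a VAS-F x group x time term, which might be added because the research questions ask whether fatigue modulates the group differences. Group x time would then also be evaluated at zero VAS-F change. The plan does not state such a term.

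Two further limits stand. Zero need not lie outside the data: under a normal distribution with mean 2 and SD 1.5, about 9% of participants fall below it, and with mean 1 about 25%. And a raw test that finds improvement is not a false positive for the quantity it tests, since accuracy may truly rise at zero build-up. The error lies in reading that result as the average change.

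**Conclusion.** The point holds in conditional form, as a free improvement. If VAS-F change is entered raw and crossed with time, the within-group time (or subphase) effect describes someone with no fatigue build-up, and can miss or reverse a real average change. In the worked case the loss runs from none at a mean VAS-F change of 0 to a fall from about 78% to 8% at a mean of 2. With no correlation it is milder, from about 75% to 35%. The size depends on the ratio of the VAS-F mean to its SD and on the correlation with accuracy change. The documents give none of these, and they may differ between tasks. The study is described as exploratory and the effect carries no hypothesis of its own. It will still be reported, because the plan commits to studying accuracy within groups and over time.

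**What to change.** In both the Part A and the Part B paragraphs of Data and statistical analysis, state that:
- VAS-F change is centred at its overall mean, both groups together, separately for each task;
- it is crossed with time;
- it is, or is not, crossed with group (and so whether a VAS-F x group x time term is fitted).

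Report the time effect from the centred model, and also from the model without the covariate. The cost is a sentence or two in each paragraph. No new data are needed, and the group x time and VAS-F x time tests are unchanged by the centring as long as no three-way term is fitted.

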During the experimental perceptive task the imposed speed will vary from the baseline in an upward/downward fashion with fixed increments (of 0,028m/s) but with randomized time in between every acceleration: the increase in speed will continue for 15 consecutive incremental steps, although never trespassing the participant's maximal speed (derived from their overground performance in first minute of 6MWT, see above), it will stabilize on that value before decreasing toward the baseline speed (with the same number of consecutive steps). As demonstrated in the example, in figure 5, this protocol will last 6 minutes and will impose the absolute magnitude of speed changes (0,42 m/s) for all participants and it will be divided in 3 phases: 1 minute of stable comfortable speed, 150 seconds of speed increments and 150 seconds of speed decrements. The randomization procedure for the time in between every speed variation will ensure that each speed level lasts between 5 and 15 seconds. Each verbal report given by the participants will be immediately recorded by the experimenter.

Obtaining a continuous report of the perceived treadmill speed and confronting it with the actual one will allow us to calculate an intra-subject correlation coefficient between perceived and actual speed, reflecting perceptive correspondence accuracy. This degree of correspondence may vary within a performance and therefore the minute by minute or protocol subphases accuracy dynamics will be also studied (see 'Data and statistical analysis').

[figure not shown]

Figure 9 Perceptive accuracy for imposed speed variations during treadmill walking: Task 1 illustration, wearables placement and Perception vs Performance plot graphic illustration (example pattern of imposed speed).  $\Delta_{min1-6}$  indicates that within-protocol variability in the intrasubject correlation will be studied for the different subphases of the protocol.

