### **Research questions for Part B – ‘Perception of imposed performance variations’**

- Do PwMS with and without reported fatigue, and HC differ in their perceptive accuracy for imposed walking speed variations during treadmill-based experimental protocols? Are these difference modulated by the accumulation of fatigue during the course of the protocol?
- Do PwMS with and without reported fatigue, and HC differ in their perceptive accuracy for imposed STS vertical excursion variations during self-paced experimental protocols? Are these difference modulated by the accumulation of fatigue during the course of the protocol?
- Are these difference modulated by time (different subphases) within the course of the protocol?
- Do PwMS and HC differ in the correspondence between measured and subjective (i.e. confidence rating) dimensions of perceptive accuracy?

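### Part B's per-phase correlation is undefined in the treadmill's constant first minute and, in the other phases, measures tracking of changes rather than agreement with the imposed level

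*Combined protocol and SAP*

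**What the plan says.** Experimental design Part B, Task 1, describes a six-minute treadmill protocol: "it will be divided in 3 phases: 1 minute of stable comfortable speed, 150 seconds of speed increments and 150 seconds of speed decrements". Participants report perceived speed every 10 seconds on a personal scale from 0 (comfortable) to +100 (maximal). "Each verbal report given by the participants will be immediately recorded by the experimenter". The section plans an "intra-subject correlation coefficient between perceived and actual speed, reflecting perceptive correspondence accuracy" and adds that the "minute by minute or protocol subphases accuracy dynamics will be also studied". Task 2 plans the same for seat height, on a scale from 0 to -100.

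Data and statistical analysis then states: "These correlations will be examined separately for different phases of each trial to index perceptive accuracy". The values are Fisher-transformed and studied "using a mixed model ANOVA with time (protocol subphase) and group as factors".

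The Part B hypotheses expect the deficit of people with MS (PwMS) to be larger in the last subphase, on the way back from the hardest level. The Introduction defines accuracy as how truthful perception is against performance, and mentions misjudgement in both directions.

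The only difference score in Part B is this: "The correspondence between measured and reported dimensions of perceptive accuracy will be calculated as their absolute difference". The Part B research questions show that it concerns "correspondence between measured and subjective (i.e. confidence rating) dimensions of perceptive accuracy", not reported against imposed level. No section excludes the constant minute, and none plans a reported-minus-imposed error.

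**The concern.** There are two separate problems.

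- **Treadmill only.** A correlation needs variation in both variables. In the first phase the imposed speed does not vary, so one level of the group-by-subphase analysis is empty for everyone, and the plan does not say what enters the ANOVA.
- **Both tasks.** Within a phase the correlation ignores a constant offset. Suppose PwMS keep reporting a faster belt or a lower seat than imposed while the level returns to comfortable, yet follow the direction of change. They can then score as well as controls in the very subphase where the protocol expects them to be worse. Where the correlation does fall, it does not say whether reports were too high or too low.

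**Working it through.** **1. The plan's own figures.** 60 + 150 + 150 = 360 s = 6 min, and 15 × 0.028 = 0.42 m/s; both reproduce. One report per 10 s gives 60/10 = 6, 150/10 = 15 and 150/10 = 15 reports, 36 in all.

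**2. Constant phase.** r = cov(x, y) / (SD_x × SD_y), with x imposed and y reported. In phase 1, SD_x = 0 and cov = 0, so r = 0/0 for all 6 reports of every participant. The same holds for a rank correlation and for minute 1. This needs no assumption.

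**3. Constant shift.** Replacing y by y + c leaves cov and SD_y unchanged, so r is unchanged, while mean(y − x) rises by c. In one simulated participant (noise SD 10, unbounded reports), r in phases 2 and 3 was 0.980 and 0.973 both before and after +20. Mean signed error over the three phases went from +5.3, −2.1, −1.8 to +25.3, +17.9, +18.2.

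**4. Bounded scale, single participants.** Assumed: noise SD 5 or 10 points, reports limited to 0–100, level durations 5–15 s summing to 150 s per ramp. The peak is 0.42 divided by the personal range: 0.42/1.2 = 35%, 0.42/0.8 = 52.5%, 0.42/0.6 = 70%, 0.42/0.42 = 100%.

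Decrement phase, peak 52.5%, noise SD 5:

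| Shift | r | Mean signed error |
|---|---|---|
| 0 | 0.956 | +0.3 |
| +20 | 0.954 | +20.0 |
| −10 | 0.942 | −8.1 |
| −20 | 0.882 | −14.6 |

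- Over peaks 35–70% and both noise levels, +10 or +20 changes r by at most about 0.005. A shift of −10 lowers it by 0.008–0.038 and −20 by 0.037–0.193, because reports hit the floor at 0.
- At peak 100% (noise SD 5), +20 moves r from 0.987 to 0.984.
- Sit-to-stand return phase, noise SD 5, 20 points away from 0: r 0.987 to 0.984 (seat range 120–80% of lower leg length) or 0.988 to 0.988 (100–80%). With 20 points towards 0, r is 0.969 or 0.957.

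**5. 40 versus 40, decrement-phase Fisher z, t-test at 0.05.** Person-to-person SD of the shift is assumed at 5–15. The table gives the share of studies showing PwMS as less accurate (2.5% expected by chance):

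| Case | Shift | Share |
|---|---|---|
| Peak below the end of the scale | +10 or +20 | about 0–4% |
| Peak 52.5% | −10 | 23–90% |
| Peak 52.5% | −20 | 89–100% |
| Range exactly 0.42 m/s (peak 100%) | +10 | 2–4% |
| Range exactly 0.42 m/s (peak 100%) | +20 | 14–81% |
| Range 0.35 m/s, capped plateau running on into the decrement phase | +10 | 13–84% |
| Range 0.35 m/s, capped plateau running on into the decrement phase | +20 | 71–100% |

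The capped figure depends on how the descent is run: with all 15 downward steps starting at 210 s, one run gave 3–43% at +20. At peak 52.5%, mean signed error detects 10 points either way in 81–100% of studies and 20 points in 100%; absolute error detects −10 in 2–100%.

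**6. Group × subphase contrast** (decrement minus increment, shift in the last phase only, peaks 35–70%). Fisher z: 0–3% at +10 or +20, 12–71% at −10, 35–100% at −20. Signed error: 71–100% for 10 points, at least 99% for 20. If half of PwMS shift +20 and half −20, signed error finds it in 0–6% and absolute error in 33–100%.

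**7. Whole-trial r.** A +20 shift in the last phase only lowers it from 0.965 to 0.850 (peak 52.5%, noise SD 5). A shift present throughout leaves it unchanged, apart from truncation.

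**The case against.** The strongest reply is that tracking is the declared construct. The plan correlates imposed performance with the perception of its variations, and the research questions ask about accuracy for variations. On that reading r is a legitimate index, and it does not depend on the scale anchors. This stands, and it is why r should be kept. It does not turn r into a measure of truthfulness as the Introduction defines accuracy.

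The whole-trial coefficient does fall when only the last phase is shifted. It cannot place the error in the last subphase, however, which is what the hypothesis is about.

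Participants are told that the zero mark is their comfortable speed, so a shift from the first report on is less plausible than one arising late. That is fair. The late-shift contrast in step 6 gives the same picture.

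The empty treadmill level would show at the first run, cannot bias a result silently, and is settled by one sentence. The study is also described as exploratory. Both are true and limit the severity.

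Three stronger readings are tempting but not supported:

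- **That Part B cannot be analysed.** The increment phase, decrement phase and whole trial all remain computable, and no constant first minute is described for sit-to-stand.
- **That r is blind to every over-report.** The treadmill protocol caps speed at the personal maximum, so some participants may reach +100, and the seat always goes down to its lowest level. Truncation there lowers r slightly, and a group difference can become detectable.
- **That signed error should replace r or rank first.** The hypothesis has no direction, the Introduction expects both directions, and signed error misses mixed shifts.

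**Conclusion.** The point holds in two parts. The treadmill phase-1 and minute-1 correlations are undefined in all participants; this is certain. In the remaining phases of both tasks, per-phase r measures tracking, is invariant to a constant shift of unbounded reports, and never gives the direction or size of an error; this is also certain.

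The last-subphase hypothesis can therefore miss a real loss of truthfulness. How often depends on the scale. A shift away from 0 is practically invisible while reports stay clear of the far end, and partly to largely detected, without direction, when the imposed level reaches it. A downward treadmill shift is partly to largely registered through the floor at 0.

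Confidence in these magnitudes is moderate. Noise, peak and between-person SD are assumed, and the documents do not give the spread of personal ranges. The group simulations cover the treadmill only. Undefined correlations were left out of them (up to 25% of shifted PwMS in the step 6 contrast at −20, peak 35%). This should be fixed, but it does not invalidate Part B.

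**What to change.** In Data and statistical analysis, experimental Part B:

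- State that per-phase correlations are computed only where the imposed level varies. For the treadmill, enter the increment and decrement phases in the correlation ANOVA and drop the phase-1 and minute-1 correlations.
- Keep Fisher-z r as the tracking measure.
- For both tasks, co-report the mean signed and the mean absolute reported-minus-imposed difference on the personal scale, per subphase, analysed by group, subphase and their interaction. Rank neither above the other: signed error gives direction and size, and absolute error covers over- and under-reporters who cancel out.
- Report per group how many correlations are undefined because reports did not change.
- Before computing errors, reconcile the text that defines the scale anchors. Maximal treadmill speed is the highest speed held for at least 15 seconds of the 6MWT in the treadmill range section, but is taken from its first minute in Part B, Task 1. Baseline seat height is given as both 100% and 120% of lower leg length in Part B, Task 2.

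The cost is SAP wording and two co-reported summaries from reports and imposed levels that the protocol already collects. The price is a few more exploratory tests, and error measures that, unlike r, can be interpreted only once the anchors agree.

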## Clinical assessment + familiarization

- **Clinical assessment**

The participants will be contacted to verify their interest and eligibility (inclusion and exclusion criteria) to participate in the study. In the case of inclusion in the study, demographic data will be recorded via web-based secured digital surveys (Castor® web application) and filled in by the examiner, including: 'Sex', 'Age', 'Body Mass Index', 'Work status', 'Year from diagnosis' (if living with a chronic condition, specifying the subtype when relevant), 'Use of assistive device for walking in daily life', 'Use of medications' (that could influence fatigue, motor or cognitive performance).

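### The predictor regression has no selection rule, size limit or validation for about 30 candidates and 40 people per group, so its predictors and R² will be inflated

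*Combined protocol and SAP*

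**What the plan says.** The final paragraph of Data and statistical analysis has two steps. In the first, for the accuracy outcomes of Parts A and B, "we will explore correlations, separated per group, to investigate the relationship between objectively measured perceptive accuracy and factors that potentially interfere with it". The factors are described only as "demographics, questionnaires and clinical assessments". The second step, introduced by the word *then*, is a regression meant to measure how strong these relationships are and to "identify the most important explanatory factors or predictors".

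The same section says that alpha "for all analyses will be set at 0,05". The Participants section sets the sample at "44 PwMS and 44 healthy controls (40, +10% to cover possible dropouts and missing data").

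The plan does not give a closed list of candidates, a rule for entering them, a maximum model size, a multiplicity adjustment, shrinkage, or internal or external validation. It also does not say whether the regression is run per group or on both groups together. Only the correlations are described as separate by group.

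**The concern.** The number of candidate factors is close to the number of people in each group. When many candidates are examined and a regression is fitted to the same participants without a fixed list or a correction, some candidates look important by chance. The R² then credits the model with explaining that chance variation.

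The results at stake are the ones this step exists to produce: the strength of the relationships and the ranking of predictors. A report could name, say, a fatigue scale or a balance test as a leading determinant of perceptive accuracy when there is no relationship. Later studies could then be designed around it.

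**Working it through.** **Inputs from the documents**
- Analysable sample: 40 per group. The recruitment figure reproduces: 40 × 1.10 = 44.
- Alpha: 0.05 for every analysis. Two-sided testing is assumed because sidedness is not stated.
- Candidates, counted as one total score per instrument:
  - Demographics, both groups: sex, age, BMI, work status, education, medication = 6.
  - MS characteristics, PwMS only: "EDSS, type of MS, use of assistive device for walking in daily life, and years since diagnosis" = 4.
  - Questionnaires, both groups: GLTEQ, PSQI, GSE, CSD, BPI, FES-I, HADS, PANAS, FSMC, MFIS, MAIA-2, ISAQ, PAS = 13. MSSE-c and MSWS-12 add 2 in PwMS.
  - Tests: SDMT, BVMT-R, T25FW, proprioception quotient, Rate of Perceived Stability, 6MWT, 30CST, DJPT = 8.
  - Totals: controls 6 + 13 + 8 = 27; PwMS 6 + 4 + 15 + 8 = 33. The working value is 30. Subscores would add more.
- Accuracy outcomes: at least 6 (walking speed, STS duration, gait smoothness, STS smoothness, treadmill speed, seat height), before thresholds and subphases. This is a count from the research questions, not a figure in the plan.

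**Assumptions not in the documents**
- Candidates with a correlation below p = 0.05 go into the regression.
- The regression is run per group.
- Candidates share a common pairwise correlation ρ. No value is given, so 0 to 0.5 is shown.
- No candidate is related to the outcome (pure noise).

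**Step 1: false correlations per outcome and group**
- Expected number: 30 × 0.05 = 1.5, whatever ρ is.
- Chance of at least one if candidates are independent: 1 − 0.95^30 = 0.785 (0.750 for 27, 0.816 for 33).
- At n = 40 a correlation passes when |r| > 0.312.

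**Step 2: simulation of screening followed by ordinary least squares on the survivors** (n = 40, 30 candidates, 6,000 null runs per row)

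| ρ | Any false correlation | At least one noise predictor significant in the regression | Mean number significant | Mean R² when anything is selected |
|---|---|---|---|---|
| 0 | 0.79 | 0.71 | 1.01 | 0.23 |
| 0.2 | 0.72 | 0.54 | 0.66 | 0.21 |
| 0.3 | 0.68 | 0.45 | 0.50 | 0.20 |
| 0.5 | 0.52 | 0.27 | 0.28 | 0.18 |

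The true R² is 0 in every row.

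**Step 3: the whole plan, 6 outcomes × 2 groups = 12 analyses**
- False correlations expected: 1.5 × 12 = 18.
- Noise predictors significant after regression: 1.01 × 12 ≈ 12 at ρ = 0; 0.66 × 12 ≈ 8 at ρ = 0.2; 0.28 × 12 ≈ 3 at ρ = 0.5.
- Chance that at least one of the 12 regressions keeps a noise predictor, treating them as independent: even at ρ = 0.5, 1 − (1 − 0.27)^12 ≈ 0.98.

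**Step 4: the other reading, all candidates entered together**
- Expected noise R² = k/(n − 1) = 30/39 = 0.77 (27/39 = 0.69; 33/39 = 0.85).
- In simulation with 30 candidates at n = 40, 47% of null models had at least one coefficient with p < 0.05. The overall F test kept its 5% level.

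**Step 5: a pooled regression**
- At n = 80, 30 candidates and ρ = 0.2, the mean R² when anything is selected falls from 0.21 to 0.11. The chance of at least one false correlation stays at about 0.72.

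**The case against.** **The plan does not state the procedure simulated here.** This is correct. It does not say that correlations select the predictors or that the regression is per group. Both are assumptions. Screening is the natural reading, because the regression follows the correlations and is meant to assess the same relationships. The alternative of entering everything does not rescue the R², as Step 4 shows.

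**The study is declared exploratory.** This stands as a limit on severity. The analysis comes last, tests no listed hypothesis and does not touch the group comparisons or the mixed ANOVAs. But the label excuses a lack of confirmatory error control. It does not correct an inflated R² or ranking once these are reported.

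**Four stronger readings are tempting, and the documents do not support them.**
- A reader might infer that false predictors are near certain for every outcome. That holds only across the whole plan; for one outcome in one group the chance is 27–71%.
- A reader might carry all 18 false correlations forward as false predictors. Only about 3 to 12 remain significant in the regression.
- A reader might take a null R² of 0.30, which results from forcing the five best-correlated candidates into each model. The plan contains no such rule.
- A reader might fault the plan for not testing whether associations differ between PwMS and controls. None of its research questions or hypotheses asks this, so separate descriptive correlations are not wrong in themselves.

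**Conclusion.** The concern holds as a gap in specification that biases this step's outputs. With about 30 candidates, 40 people per group and no rule or correction, the reported strength and ranking will be too optimistic whether candidates are screened or all entered. With screening, the apparent R² from noise is about 0.18–0.23 when anything is selected. With all entered, it is about 0.77.

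The direction of the bias does not depend on the assumptions, but its size does. It rests on the total-score count of candidates, the count of six outcomes, the assumed correlation between candidates and, for the counts over 12 analyses, on per-group regression. Severity is modest: the analysis is secondary and exploratory, and the repair is cheap.

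**What to change.** Add a short paragraph to Data and statistical analysis before the data are seen:

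1. Do not choose regression predictors by univariate p-value.
2. Use one of two routes. Either pre-name a short list for each outcome, for example at most five, or keep the wide set in a penalised model (lasso or ridge).
3. On either route, report an optimism-corrected R², from the bootstrap or repeated cross-validation, with every selection or tuning step repeated inside each resample. A short list still needs this: five noise predictors at n = 40 give an expected R² of 5/39 = 0.13.
4. Present the per-group correlations as descriptive estimates with confidence intervals.
5. State whether the regression is per group or pooled. Fit measures that apply only to PwMS (MSSE-c, MSWS-12, EDSS) in PwMS only. Pooling is optional: it lowers the R² inflation but not the false-hit rate.
6. Add group interactions only if the report intends to claim that an association differs between PwMS and controls.

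No extra participants or measurements are needed. The cost is a little more analysis work and fewer predictors claimed.
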